### **Specific exclusion criteria for study participants WITHOUT hepatic insufficiency**

22. Participant has a history or presence of cardiovascular (eg, cardiac insufficiency, coronary heart disease, hypertension, arrhythmia, tachyarrhythmia, or myocardial infarction), respiratory, hepatic, renal, gastrointestinal, endocrinological, hematological, or neurological disorders capable of significantly altering the absorption, metabolism, or elimination of drugs; constituting a risk when taking the study intervention; or interfering with the interpretation of data. Symptomatic or asymptomatic orthostatic hypotension at Screening

defined as a 20mmHg or more decrease in SBP, or 10mmHg or more decrease in DBP after 1 and 3 minutes standing with the arm relaxed at the side (time zero begins after the study participant is upright). Five minutes of supine rest is used as baseline.

23. Participant tests positive for hepatitis B surface antigen, or Hepatitis C virus antibody (HCV-Ab) at Screening or within 3 months prior to the first dose of study medication.

NOTE: Participants with positive HCV-Ab due to prior resolved disease can be enrolled if a confirmatory negative Hepatitis C ribonucleic acid (RNA) test is obtained. The HCV RNA testing is optional and participants with negative HCV-Ab test are not required to also undergo Hepatitis C RNA testing.

24. Participant must have BP and pulse rate (PR) within normal range in the supine position after 5 minutes rest (SBP: 90mmHg to 150mmHg; DBP: 40mmHg to 95mmHg; PR: 40bpm to 100bpm). In case of an out-of-range result, 1 repeat will be allowed. If the readings are out-of-range again, the study participant will not be included.

25. Participant has alanine aminotransferase (ALT), aspartate aminotransferase (AST), or alkaline phosphatase (ALP) >1.0x upper limit of normal (ULN).

26. Participant has bilirubin >1.0xULN (isolated bilirubin >1.0xULN is acceptable if bilirubin is fractionated and direct bilirubin <35%).

27. Participant has current or chronic history of liver disease or known hepatic or biliary abnormalities (with the exception of Gilbert's syndrome or asymptomatic gallstones).

Note: For participants with a Baseline result >ULN for ALT, AST, ALP, or total bilirubin, a baseline diagnosis and/or the cause of any clinically meaningful elevation must be understood and recorded in the electronic Case Report Form (eCRF).

If participant has >ULN ALT, AST, or ALP that does not meet the exclusion limit at Screening, repeat the tests, if possible, prior to dosing to ensure there is no further ongoing clinically relevant increase. In case of a clinically relevant increase, inclusion of the study participant must be discussed with the UCB Study Physician.

28. Participant has tests results with ALT, AST, or ALP up to 25% above the exclusion limit may be repeated once for confirmation. This includes rescreening.

29. Participant has gastrointestinal disease with the potential to influence absorption, including motility disorders.

### **Specific exclusion criteria for study participants WITH moderate hepatic insufficiency**

Participants with moderate hepatic insufficiency will not be eligible for inclusion in this study if any of the following criteria apply at Screening or Baseline (Day -1):

30. Participant must have vital sign parameters defined as: supine BP after at least 5 minutes rest and standing after 1 and 3 minutes rest must be within normal range (SBP: 90mmHg to 180mmHg; DBP: 40mmHg to 105mmHg; PR: 50bpm to 100bpm).

31. Results of laboratory tests must be within the reference ranges except those usually found to be abnormal in study participants with moderate hepatic insufficiency. A study participant

with other values outside the normal range may be included in the study if, in the opinion of the Investigator, these values are of no clinical significance for the participant with moderate hepatic insufficiency and after approval of the UCB Study Physician has been obtained.

32. Participants with moderate hepatic insufficiency and derived and associated clinical and laboratory findings of moderate hepatic insufficiency are allowed as long as they do not have other clinically important systemic disease such as psychiatric illness, or uncontrolled diabetes (based on medical history, physical examination, ECG, and/or routine laboratory data). The study participant may not have diseases that might confound the results of the study or cause additional risks during administration of PSL.
33. Participant has acute liver failure of any etiology.
34. Participant has biliary cirrhosis.
35. Participant has used any drug indicated for the medical care of moderate hepatic insufficiency that is not established in dose and schedule for at least 14 days before the first liver function test (except paracetamol with a maximal dose of 2g/day or with a maximum of 10g over 15 days).

### **5.3 Lifestyle restrictions**

#### **5.3.1 Meals and dietary restrictions**

- Participants will complete a light meal 30 minutes prior to each morning dose of PSL and will complete a standard meal 30 minutes prior to the evening dose. The standardized meal composition and timing should be consistent for all days the participant is on study. On days when PK assessments will be taken, study participants will complete a standardized meal (same macronutrient will be administered for minimizing covariates) in the afternoon and evening.
- Padsevonil will be administered orally with 8oz (240mL) water. Between 1h predose and 2h postdose, the total intake of beverages should be limited to 100mL.
- The participant must not ingest grapefruit, starfruit, and pawpaw (as beverage, fruit, or supplements) within 72h before the study medication administration. These fruits are not allowed during the Treatment Period and throughout the study.

#### **5.3.2 Caffeine, alcohol, and tobacco**

- During dosing, participants will abstain from ingesting caffeine- or xanthine-containing products (eg, coffee, tea, cola drinks, and chocolate) for 48h before the start of dosing until after collection of the final PK sample.
- During the study, participants will abstain from alcohol for 24 hours before the start of dosing until after collection of the final PK sample.

#### **5.3.3 Activity**

- Participants will abstain from strenuous exercise for 24 hours before each blood collection for clinical laboratory tests and during the study. Participants may participate in light recreational activities during the study (eg, watching television, reading).

## 5.4 Screen failures

Screen failures are defined as participants who consent to participate in the clinical study but are not subsequently entered in the study. A minimal set of screen failure information is required to ensure transparent reporting of screen failure participants to meet the Consolidated Standards of Reporting Trials publishing requirements and to respond to queries from regulatory authorities. Minimal information includes demography, screen failure details, eligibility criteria, and any SAE.

### 5.4.1 Rescreening

Individuals who do not meet the criteria for participation in this study (screen failure) may be rescreened. Study participants may be rescreened under conditions such as the following:

- Study participant ingests grapefruit (as beverage, fruit, or supplements) within 72 hours before each administration of study medication.
- If a study participant does not meet the enrollment criteria at Screening or on Day -1 due to an out-of-range laboratory result or a minor illness, he/she can be rescreened once at the discretion of the Investigator. Provided all enrollment criteria are met at the second screening, the study participant can be included.

Study participants may be included if the repeat values for the laboratory screening criteria are within normal ranges and/or if repeat values show normalization of the out-of-range safety laboratory values, and/or after the study participant makes a complete recovery from the mild illness, and if all other screening criteria are met.

Tests that result in ALT, AST, or ALP up to 25% above the exclusion limit may be repeated once for confirmation. This includes rescreening and only applies to healthy participants.

Rescreened participants will be assigned a new participant number.

## 6 STUDY TREATMENTS

Study treatment is defined as any investigational treatment(s), marketed product(s), or placebo intended to be administered to a study participant according to the study protocol.

### 6.1 Treatments administered

A summary of the treatments administered is provided in [Table 6-1](#). Treatments will be administered in an open-label fashion and participants will be dosed in an upright position and will remain semi-recumbent until 4 hours after dosing.

**Table 6-1: Study medications administered**

Study Medication Name:	Padsevonil
Dosage formulation:	Tablets
Unit dose strength(s):	100mg
Route of administration:	Oral
Dosing instructions:	Dosing instructions are provided in the UP0056 IMP Handling Manual (IMP Instructions for Handling).
Packaging and labeling:	PSL tablets are manufactured, packaged, and labeled according to Good Manufacturing Practice guidelines and applicable laws and regulations.
Manufacturer:	UCB

IMP=investigational medicinal product; PSL=padsevonil

## 6.2 Preparation, handling, storage, and accountability requirements

The Investigator or designee must confirm appropriate temperature conditions have been maintained during transit for all study medications received and any discrepancies are reported and resolved before use of the study medication.

Only participants enrolled in the study may receive study medication and only authorized site staff may supply or administer study medication. All study medication must be stored in a secure, environmentally controlled, and monitored (manual or automated) area in accordance with the labeled storage conditions with access limited to the Investigator and authorized site staff.

The Investigator, institution, or the head of the medical institution (where applicable) is responsible for study medication accountability, reconciliation, and record maintenance (ie, receipt, reconciliation, and final disposition records).

In case an out-of-range temperature is noted, it must be immediately reported as per instructions contained in the UP0056 IMP Handling Manual (IMP Instructions for Handling).

Further guidance and information for the final disposition of unused study medication are provided in the UP0056 IMP Handling Manual (IMP Instructions for Handling).

### 6.2.1 Drug accountability

A Drug Accountability form will be used to record study medication dispensing and return information on a by-participant basis and will serve as source documentation during the course of the study. Details of any study medication lost, damaged (due to breakage or wastage), not used, partially used, disposed of at the study site, or returned to the Sponsor or designee must also be recorded on the appropriate forms. All supplies and pharmacy documentation must be made available throughout the study for UCB (or designee) to review.

The Investigator (or designee) is responsible for retaining all used, unused, and partially used containers of study medication until returned or destroyed.

The Investigator may assign some of the Investigator's duties for drug accountability at the study site to an appropriate pharmacist/designee.

The Investigator must ensure that the study medication is used only in accordance with the protocol.

Periodically, and/or after completion of the clinical phase of the study, all used (including empty containers)/partially used, unused, damaged, and/or expired study medication must be reconciled and either destroyed at the site according to local laws, regulations, and UCB standard operating procedures or returned to UCB (or designee). Investigational medicinal product intended for the study cannot be used for any other purpose than that described in this protocol.

### **6.3 Measures to minimize bias: randomization and blinding**

This study is an open-label, non-randomized study; therefore, no study personnel or study participants will be blinded and no randomization will occur.

Each participant will receive a 5-digit number assigned at Screening that serves as the participant identifier throughout the study. The participant number will be required in all communication between the Investigator and designee.

#### **6.3.1 Procedures for maintaining and breaking the treatment blind**

##### **6.3.1.1 Maintenance of study medication blind**

This is not applicable as this is an open-label study.

##### **6.3.1.2 Breaking the treatment blind in an emergency situation**

This is not applicable as this is an open-label study.

### **6.4 Treatment compliance**

Study participant compliance will be ensured by the administration of study medication by designated site personnel. Drug accountability must be recorded on the Drug Accountability form.

### **6.5 Concomitant medication(s)/treatment(s)**

#### **6.5.1 Permitted concomitant treatments (medications and therapies)**

The use of concomitant medications during this study by participants without hepatic insufficiency should be avoided unless necessary to treat AEs or unless approved on a case-by-case basis prior to enrollment (eg, hormonal contraceptives). The use of any concomitant medications should be approved by the Sponsor in advance, in writing, when possible. The following concomitant medications are permitted during the study:

- Paracetamol for the treatment of mild symptoms (eg, headache or other pain), given at most every 6h to 8h, not exceeding 2g/day, and with a total of no more than 10g over 15 days.
- Inhaled corticosteroids for seasonal rhinitis.
- Oral contraceptives not exceeding 30µg ethinyl estradiol or postmenopausal HRT or implants, patches, or IUDs/IUSs delivering progesterone (for female participants).

Use of other chronic medication by study participants with moderate hepatic insufficiency, not interfering with the endpoints of the study and at the discretion of the UCB Study Physician, will be permitted.

### **6.5.2 Prohibited concomitant treatments (medications and therapies)**

The following concomitant medications are prohibited during the study:

- With the exception of permitted concomitant treatments listed in Section 6.5.1, all prescription or nonprescription medicines are prohibited within 2 weeks or 5 half-lives, whichever is longer, of the respective drug, prior to first administration of PSL and during the study, unless required to treat an AE. This includes all over-the-counter remedies, vitamins, and herbal and dietary supplements (including St. John's Wort).
- Hepatic enzyme-inducing drugs (eg, glucocorticoids, phenobarbital, isoniazid, phenytoin, rifampicin, etc.) should not be used within 2 months prior to dosing. In case of uncertainty, the UCB Study Physician should be consulted.
- Drugs of unknown half-lives are prohibited within 2 weeks before administration of PSL and during the clinical part of the study, unless required to treat an AE.

If a study participant needs or takes any prohibited medication, the Investigator will (where possible) discuss with the UCB Study Physician and a decision will be made whether the study participant can continue in the study or must be withdrawn.

### **6.5.3 Rescue medication**

Not applicable.

### **6.6 Dose modification**

No PSL dose modifications are permitted during the study for an individual study participant.

### **6.7 Treatment after the end of the study**

There are no plans for participant continued care after the end of the study.

## **7 DISCONTINUATION OF STUDY MEDICATION AND PARTICIPANT DISCONTINUATION/WITHDRAWAL**

### **7.1 Discontinuation of study medication**

Study medication will be stopped if the study participant develops a medical condition (or laboratory abnormality or ECG change) that, in the opinion of the Investigator, compromises the study participant's ability to participate or safety.

In all cases the study participant should be followed until the condition has resolved as agreed by the Investigator and the UCB Study Physician. Investigators should contact the UCB Study Physician, in advance, whenever possible, to discuss the withdrawal of a participant. No restart will be allowed.

#### **7.1.1 Liver chemistry stopping criteria**

The liver stopping criteria in this study will differ between those participants with normal hepatic function and those with impaired hepatic function.

[figure not shown]
##### **7.1.1.1 Participants with normal hepatic function**

Discontinuation of study medication for abnormal liver function should be considered by the Investigator when a healthy participant meets 1 of the conditions outlined in Figure 7-1 or if the

Investigator believes that it is in best interest of the participant. Study medication will be discontinued immediately and permanently for a healthy participant if liver chemistry stopping criteria are met.

If clinically concerning deteriorations in liver chemistry findings occur in a participant with established moderate hepatic insufficiency, then study medication will be discontinued immediately and permanently.

**Figure 7-1: Liver chemistry stopping algorithm**

ALT=alanine aminotransferase; AST=aspartate aminotransferase; INR=international normalized ratio; SAE=serious adverse event; ULN=upper limit of normal

Specific assessments and follow up actions for potential drug-induced liver injury (PDILI) are provided in Appendix 6 (Section 10.6).

### 7.1.1.2 Participants with impaired hepatic function

In view of the differing degrees of hepatic impairments anticipated among this subset of participants, the fixed criteria detailed in Figure 7-1 are inappropriate.

Accordingly, any significant elevation of AST, ALT, bilirubin, or international normalized ratio (INR) values should be discussed with the UCB Study Physician and, in the context of the Baseline and pre-study levels typical for the individual and their overall clinical condition, a decision reached as to whether the case should be handled as a PDILI.

As a guide, a doubling of any value is expected to represent a threshold for this evaluation.

If a PDILI case is so identified, then the participant will be evaluated in accordance with the requirements of Appendix 6 (Section 10.6), adapted as necessary to match the circumstances.

### **7.1.2 Criteria for study hold due to adverse events**

In recognition of the advanced status of the development program for PSL, the following study hold/stopping rules will apply to this study.

In the event that either or both of the following criteria are met, a safety review will be immediately initiated:

- The occurrence of a serious adverse reaction (SAR) (ie, an SAE considered at least possibly related to the study medication) in 2 study participants, where those SARs occur in the same body system.
- The occurrence of a severe nonserious adverse reaction (ie, severe nonserious AEs considered at least possibly related to the study medication) in 3 study participants, where those severe ARs
  - occur in the same body system, and
  - lead to the withdrawal of the affected participant

The safety review will be conducted by an internal, study-specific Safety Monitoring Committee comprised of the Investigator and appropriate members of the UCB Study Team (such as Study Physician, Safety Physician, Clinical Project Manager, Clinical Pharmacologist), as quickly as possible, to review the available data and determine whether it is appropriate to continue dosing at the next scheduled dosing point. This will take the form of a risk/benefit evaluation from the perspective of the individual study participants. In making this evaluation, account will be taken of the potential risks of sudden discontinuation of study medication, particularly in participants who may be taking higher dose levels, and whether or not a tapering period, and its duration/speed, should be undertaken.

The Safety Monitoring Committee will also decide whether it is appropriate to continue the study with or without dose adaptations, additional safety assessments, or other changes in design. If such changes are deemed necessary to protect the wellbeing of participants, further dosing in the study will be suspended while a substantial amendment is submitted to the Country(ies) Health Authority and Research Ethics Committee(s) and the study will not restart until that amendment has been approved.

If the Safety Monitoring Committee cannot be convened before the next scheduled dosing point, the Investigator will make an independent evaluation as to whether it is appropriate to continue dosing pending the review.

Detailed procedures for reporting SAEs and other safety events which may meet study hold/stopping criteria are provided in Appendix 3 (see Section 10.3).

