10. The study participant has active suicidal ideation without a specific plan as indicated by a positive response ("Yes") to Question 4 of the "Since Last Visit" version of the C-SSRS. The study participant should be referred immediately to a mental healthcare professional and may be withdrawn from the study based upon the Investigator's judgment of the benefit/risk of continuing the study participant in the study on PSL.
11. The study participant has active suicidal ideation with a specific plan as indicated by a positive response ("Yes") to Question 5 of the "Since Last Visit" version of the C-SSRS. The study participant should be referred immediately to a mental healthcare professional and must be withdrawn from the study.
12. The study participant is suspected of having a serious multiorgan hypersensitivity reaction. Serious suspected multiorgan hypersensitivity cases may be identified and reported to the Sponsor by the Investigator using the following algorithm:
  - An AE or laboratory value (as defined below) suggestive of internal organ involvement including but not limited to hepatitis, nephritis, pneumonitis, carditis, colitis, encephalitis, pancreatitis, myositis, arthritis, or hematologic system involvement combined with at least 1 of the following: fever, rash, lymphadenopathy, or eosinophilia.

- Treatment-emergent abnormal laboratory value criteria suggestive of internal organ involvement or eosinophilia:
  - Eosinophils percentage  $\geq 10\%$ .
  - Eosinophils absolute  $\geq 0.5\text{G/L}$ .
  - Neutrophils absolute  $< 1.5\text{G/L}$ .
  - Platelets absolute  $\leq 100\text{G/L}$ .

Investigators should attempt to obtain follow-up information on study participants in the case of withdrawal.

Investigators should contact the UCB Study Physician, whenever possible, to discuss the withdrawal of a participant in advance.

Participants who are withdrawn will be replaced at the discretion of the Investigator and Sponsor.

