##### **8.5.1 Time period and frequency for collecting AE and SAE information**

All AEs and SAEs will be collected from the signing of the ICF and at the time points specified in the Schedule of Activities ([Table 1-3](#)).

Medical occurrences that begin before the start of study medication, but after obtaining informed consent will be recorded on the Medical History/Current Medical Conditions section of the eCRF, not the AE section.

All SAEs will be recorded and reported to the Sponsor or designee within 24h, as indicated in Appendix 3 (Section [10.3](#)). The Investigator will submit any updated SAE data to the Sponsor within 24h of it being available.

The Investigator is specifically requested to collect and report to UCB (or its representative) any SAEs (even if the Investigator is certain that they are in no way associated with the study medication), up to 30 days from the end of the study for each participant, and to also inform participants of the need to inform the Investigator of any SAE within this period. Serious AEs that the Investigator thinks may be associated with the study medication must be reported to UCB regardless of the time between the event and the end of the study.

The method of recording, evaluating, and assessing causality of AE and SAE and the procedures for completing and transmitting SAE reports are provided in Appendix 3 (Section [10.3](#)).

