### **8.6 Safety signal detection**

Selected data from this study will be reviewed periodically to detect, as early as possible, any safety concern(s) related to the study medication so that Investigators, study participants, regulatory authorities, and IRBs/IECs can be informed appropriately.

The UCB Study Physician or medically qualified designee/equivalent will conduct an ongoing review of SAEs and perform ongoing SAE reconciliations in collaboration with the PS representative.

As appropriate for the stage of development and accumulated experience with the study medication, medically qualified personnel at UCB may identify additional safety measures (eg, AEs, vital signs, laboratory or ECG results) for which data will be periodically reviewed during the course of the study.

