**e. Is a congenital anomaly/birth defect**

**f. Important medical events:**

- Medical or scientific judgment should be exercised in deciding whether SAE reporting is appropriate in other situations such as important medical events that may not be immediately life-threatening or result in death or hospitalization but may jeopardize the participant or may require medical or surgical intervention to prevent one of the other outcomes listed in the above definition. These events should usually be considered serious.

Examples of such events include, but are not limited to, potential Hy's Law, invasive or malignant cancers, intensive treatment in an emergency room or at home for allergic bronchospasm, blood dyscrasias or convulsions that do not result in hospitalization, or development of drug dependency or drug abuse.

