#### Assessment of Intensity

The Investigator will make an assessment of intensity for each AE and SAE reported during the study and assign it to one of the following categories:

- **Mild:** An event that is easily tolerated by the participant, causing minimal discomfort and not interfering with everyday activities.
- **Moderate:** An event that causes sufficient discomfort and interferes with normal everyday activities.
- **Severe:** An event that prevents normal everyday activities. An AE that is assessed as severe should not be confused with a SAE. Severe is a category utilized for rating the intensity of an event; and both AEs and SAEs can be assessed as severe.
- An event is defined as 'serious' when it meets at least one of the predefined outcomes as described in the definition of an SAE, NOT when it is rated as severe (eg, a severe AE may be either serious or not serious, depending on whether these criteria are also met).

The National Cancer Institute Common Terminology Criteria for Adverse Events should be used as a supportive standardization instrument to evaluate AEs and SAEs, but the final intensity grading by the Investigator must be mild, moderate, or severe.

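### The safety-review trigger in Protocol 7.1.2 misses one mixed cluster: three withdrawals for severe related reactions in one body system, exactly one of them serious

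*Protocol*

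**What the plan says.** Protocol section 7.1.2 gives two criteria and states the consequence: "In the event that either or both of the following criteria are met, a safety review will be immediately initiated".

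- **First criterion:** "an SAE considered at least possibly related to the study medication) in 2 study participants", in the same body system. Neither severity nor withdrawal is required.
- **Second criterion:** "severe nonserious AEs considered at least possibly related to the study medication) in 3 study participants", in the same body system, each leading to withdrawal of the participant affected. The restriction to nonserious events appears both in the criterion and in its explanatory bracket, so it is not a slip in one place.

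No sentence lets a serious reaction count toward the three, and none combines the two counts. Protocol section 9.7 plans no interim analysis or data monitoring, and SAP section 4.5 says the same, so these are the only pre-specified event counts that oblige a review.

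**The concern.** A safety trigger should be monotone: if a set of cases is enough to require a review, the same set with one case made worse should also be enough. Here it is not. Three severe nonserious withdrawals oblige the review. If one of those three reactions is serious as well as severe, the obligation lapses, because one serious case is below two and two nonserious cases are below three.

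The mixed cluster can occur under the protocol's own definitions. Appendix 3 (section 10.3.3) rates intensity and seriousness separately and notes that "both AEs and SAEs can be assessed as severe". Section 10.3.2 lists "blood dyscrasias or convulsions that do not result in hospitalization" among events usually treated as serious, while another severe reaction in the same body system may be nonserious. Appendix 3 does not conflict with 7.1.2; it only shows that the case is possible.

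At stake is whether the committee review, which decides on dosing at the next scheduled dosing point and on changes to the study, is automatic or left to judgment. The protocol expects higher exposure, and possibly lower tolerance, in the hepatically impaired cohort (section 4.3).

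**Working it through.** The documents give no operating characteristic for this rule, so there is no stated figure to reproduce.

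**Inputs from the documents:** thresholds of 2 and 3 with their conditions (Protocol 7.1.2); up to N = 24 participants (Protocol 1.1 and 9.8).

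**Assumed inputs, not in the documents:** r, the chance per participant of a severe related reaction in one given body system that leads to withdrawal; q, the share of those reactions that are serious.

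**Step 1: the rule.** Place each participant in at most one class, all reactions being related and in one body system:

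- a = serious and severe, leading to withdrawal
- b = any other serious reaction
- c = severe nonserious, leading to withdrawal

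Current rule: a + b ≥ 2 or c ≥ 3.

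Three withdrawn cases with b = 0:

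| Serious (a) | Nonserious (c) | Review mandatory? |
|---|---|---|
| 0 | 3 | yes (c ≥ 3) |
| 1 | 2 | **no** (1 < 2 and 2 < 3) |
| 2 | 1 | yes (a ≥ 2) |
| 3 | 0 | yes (a ≥ 2) |

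With four or more withdrawn cases every split triggers.

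**Step 2: the amended rule.** a + b ≥ 2 or a + c ≥ 3. Over all (a, b, c) with a + b + c ≤ 24, the amendment adds exactly one combination, (1, 0, 2), and loses none.

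**Step 3: share missed, given exactly three such cases.** 3q(1 − q)²:

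- q = 0.1: 3 × 0.1 × 0.81 = 0.243
- q = 0.2: 3 × 0.2 × 0.64 = 0.384
- q = 1/3: 3 × (1/3) × (4/9) = 0.444
- q = 0.5: 3 × 0.5 × 0.25 = 0.375

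**Step 4: unconditional probability of the missed combination.** With no class-b reactions, P = 24 × C(23,2) × (rq) × [r(1 − q)]² × (1 − r)²¹, where C(23,2) = 253:

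| r | q = 0.1 | q = 0.2 | q = 1/3 | q = 0.5 |
|---|---|---|---|---|
| 1% | 0.04% | 0.06% | 0.07% | 0.06% |
| 2% | 0.26% | 0.41% | 0.47% | 0.40% |
| 5% | 2.1% | 3.3% | 3.8% | 3.2% |
| 10% | 5.4% | 8.5% | 9.8% | 8.3% |

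**Step 5: chance that a review is triggered, r = 5%, no class-b reactions.**

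| q | Current | Amended |
|---|---|---|
| 0 | 11.6% | 11.6% |
| 0.1 | 9.7% | 11.8% |
| 0.2 | 9.2% | 12.5% |
| 1/3 | 10.2% | 14.1% |
| 0.5 | 13.9% | 17.2% |

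The current rule becomes less likely to trigger as q goes from 0 to 0.2, although the cases are getting worse. The amended rule rises throughout.

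**Step 6: sensitivity to class b.** Steps 4 and 5 set b to zero, which makes the gap as large as it can be for given r and q. If class-b reactions are as frequent as class a, the missed combination at r = 5% has probability 1.9%, 2.6%, 2.6% and 1.8% for q = 0.1, 0.2, 1/3 and 0.5. The current rule's trigger probability is then 11.6% at q = 0, 11.3% at q = 0.1 and 14.7% at q = 0.2, so the fall in step 5 almost disappears while the gap stays.

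**The case against.** The strongest case against accepts the literal reading and disputes its weight.

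- **Rarity.** The dose is 4-fold below the maximum tolerated dose, with at most 6 days of exposure. A rate of 5% or 10% implies 1.2 or 2.4 participants of 24 withdrawn for severe related reactions in one body system, and nothing in the documents supports that. This stands: at 1% to 2% the gap has probability below 0.5%. The conditional shares apply only once exactly three such cases exist, which has probability 0.16% at r = 1% and 1.06% at r = 2%.
- **Other serious reactions.** Setting b to zero overstates the gap and the fall in trigger probability. This stands as a limit on the illustrations, as step 6 shows, but not on the defect.
- **Other safeguards.** Section 8.5.1 says "All SAEs will be recorded and reported to the Sponsor or designee within 24h"; section 7.2 says "Investigators should contact the UCB Study Physician, whenever possible, to discuss the withdrawal of a participant in advance"; under section 8.6 the Study Physician or a designee "will conduct an ongoing review of SAEs and perform ongoing SAE reconciliations", and selected data are reviewed periodically. Section 8 asks for immediate discussion of safety concerns. There is one site, and participants stay in the clinic until Day 18. The likely committee members would know of all three cases, and a discretionary review is not forbidden. So the cluster is unlikely to go unseen. However, none of these provisions obliges a committee review at any count.
- **Partial fix.** Two severe nonserious withdrawals plus one serious reaction that is not severe, or did not lead to withdrawal, would still not trigger. That is true, but this cluster is not strictly worse than three severe nonserious withdrawals, so leaving it out does not break monotonicity. Covering it is for the sponsor to decide.

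**Conclusion.** The concern holds on the text. The mandatory trigger is non-monotone at exactly one point: moving from three severe nonserious withdrawals in one body system to two plus one serious removes the obligation to review. A fourth qualifying withdrawal, or a second related serious event in that body system, closes the gap. So would a separate qualifying nonserious reaction in the participant with the serious one, a case the one-class-per-participant count leaves out.

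The practical size is small if such reactions are rare and reaches a few percent only at an assumed rate of about 5%. The conclusion about the rule needs none of these rates. The consequence is a review that is no longer automatic; no endpoint, estimate or individual stopping rule is affected. It should still be corrected, because a stated safety rule gives the wrong answer in a case it would be expected to cover, and the correction is simple.

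**What to change.** In the second criterion of Protocol section 7.1.2, remove the restriction to nonserious events in both places where it appears, and state that severe related reactions count whether serious or nonserious. Leave the first criterion, the thresholds of 2 and 3, the same-body-system condition and the withdrawal condition unchanged.

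The cost is one clause and an occasional extra internal review: at r = 2% and q = 0.2, with no class-b reactions, the chance of a review rises from 1.06% to 1.47%. It needs no additional participants, visits or tests.
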